Short term effect of smoking cessation on human metabolism

Authors: [name], [name] and [name]

Helsinki Committee approval number (Meuhedet HCO, Israel): 05-23-03-16

Date of the approval: 14/4/2016.

Date of beginning of recruitment: 18/4/2016

METHODS

The trial was designed as a two-arm study - prospective and retrospective. The study was approved by the Meuhedet HMO Ethics Committee according to the ethical guidelines of the Helsinki Committee.

Prospective Arm

Studied population

The prospective arm included 108 participants aged 30-70 who were recruited from the smoking cessation workshops of the Meuhedet HMO (Israeli Health Services) during 2016-2017. Candidates with benign tumors, bariatric surgeries, and endoscopic bariatric procedures before or during the study period were excluded.

Study design

All subjects signed informed consent to participate, after receiving detailed information about the study objectives and procedure. The collected data included weight, BMI, waist circumference and Waist Hip Ratio (WHR) at 3 time points: a. the third weekly meeting of the cessation workshop, pre-cessation phase (baseline- **phase 0**), b. workshop's last meeting (the eighth weekly cessation meeting – **phase 1**) and 6 months after the cessation program (**phase 2**). The effects of smoking cessation support medicines was also examined.

Anthropometric measurements

Weight was measured with participants standing up, wearing light clothes and without shoes, using a digital scale. Waist circumference was measured above

the iliac crest. Hip circumference was taken at the maximum circumference between the groin and the iliac crest. Height data were based on participants' self-report. Participants were classified as smokers (S), quitters (Q) and resmokers "relapsers" (RS) based on self-reported data at each visit. Participants also completed a questionnaire regarding cigarette-smoking habits and health information. The numerical value of pack years was calculated based on that questionnaire (Pack years is a unit quantifying the lifetime exposure to smoking, calculated by multiplying the number of packs of cigarettes smoked per day by the number of years the person has smoked).

Retrospective Arm

Studied population

The retrospective arm presented a file review of 200 patients between 25-70 years of age, who participated in smoking cessation workshops of the Meuhedet HMO in 2014.

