Candidates with benign tumors, bariatric surgeries, and endoscopic bariatric procedures before or during the study period were excluded, as well as those who were unavailable for a phone conversation.

Study design

Two blood test results, as documented in medical files, were collected and analyzed. The first one during the year preceding the smoking cessation workshops (baseline- **phase 0**), and the second during the year after completing them. Smoking status was verified by a telephone call. Participants were classified as smokers (S) and quitters (Q). The effect of smoking cessation medications on metabolic profile was also examined.

Metabolic measurements

File recorded blood measurements were used for Fasting Glucose (BFG), Total Cholesterol (TC), HDL Cholesterol (HDL), LDL Cholesterol (LDL) and triglycerides (TG) as examined in HMO laboratories. Results were analyzed according to WHO criteria.

STATISTICAL ANALYSIS

Data was analyzed using JMP Pro 12 and R software. Mean values and their standard error (SE) were used to summarize the distribution of continuous variables. To determine significant statistical differences between two sets of data with normal distribution we used Student's t-test/ ANOVA. For paired sets of data that may not be normally distributed we used the Wilcoxon signed rank test, and for unmatched sets-, the Mann Whitney's u-test was used. Each patient constituted his own control – each post workshop result was compared with the pre workshop result.

Fisher's proportion test was used to determine significant statistical differences between proportions in a given compatible groups. P<0.05 was considered significant. All statistical tests were two tailed.

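### SE is used to describe distributions, and the 6-month result in the prospective arm omits anyone lost before phase 2 without drawing on their phase 1 value

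*Combined protocol and SAP*

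**What the plan says.** **Design (Prospective Arm, Study design).** "The collected data included weight, BMI, waist circumference and Waist Hip Ratio (WHR) at 3 time points": phase 0 before cessation, phase 1 at the last workshop meeting, and phase 2 "6 months after the cessation program". Under Anthropometric measurements, people are classed as smokers, quitters or relapsers "based on self-reported data at each visit".

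**Tests (STATISTICAL ANALYSIS).** Each participant is their own control, and "each post workshop result was compared with the pre workshop result". The sentence on normal data opens with "To determine significant statistical differences between two sets of data with normal distribution we used" and then names the t-test, with ANOVA beside it. Paired data that may not be normal go to the Wilcoxon signed rank test. ANOVA appears only in that two-set sentence, and its form is not given. The section names no repeated-measures or mixed model, no imputation and no rule for missing visits.

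**Summary statistics (same section).** "Mean values and their standard error (SE) were used to summarize the distribution of continuous variables".

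The plan states no attrition, SD, correlation or sample-size calculation. It gives 108 participants in the prospective arm without saying whether they were enrolled or completed.

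**The concern.** There are two separate faults.

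**SE as a descriptive summary.** A distribution is described by its spread. SE shrinks with n however much individuals differ, so a reader who takes the printed figure as spread will think participants far more alike than they are. This affects both arms.

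**Unused information at 6 months.** A paired 0-to-2 test, t or Wilcoxon, needs both values. A person lost before phase 2 drops out of it, and what was seen of them at phase 1 does not help to estimate the 6-month change. If ANOVA means the classical repeated-measures form, it keeps only people with all three visits, so the same people are lost. If those who leave differ in early weight change from those who stay, the completers' mean 6-month change is biased. It is too low if early gainers leave more and too high if they leave less. The size of the weight change and its confidence interval are at stake.

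**Working it through.** The plan has no figure of its own to reproduce on this point. Only n=108 and n=200 come from the documents; every other input below is assumed.

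**1. SE against SD.** SE = SD/√n. √108 = 10.4 and √200 = 14.1. With an assumed mean change of 3.0 kg and SD of 3.0 kg at n=108, SE = 3.0/10.4 = 0.29, so the result prints as 3.0 ± 0.29. If the changes are normal, the share who do not gain is Φ(−3/3) = 16%, and the share who gain over 5 kg is 1 − Φ((5−3)/3) = 25%.

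**2. Pairs left for the 6-month test.** 108 × (1 − d) for assumed loss d of 10/20/30/40% gives 97/86/76/65. The SE rises by √(108/m), where m is the number of pairs left: 1.055/1.121/1.192/1.289.

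**3. Dropout tied to early gain.** Inputs: true mean gain 1.5 kg early and 3.00 kg at 6 months, SDs 1.5 and 3 kg, correlation 0.6, and log-odds of missing phase 2 of b per kg of early gain.

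- Hand check at 30% missing and b = +0.35. To first order, the completers' mean early gain shifts by −b × P(missing) × variance = −0.35 × 0.30 × 1.5² = −0.236 kg. The slope of 6-month gain on early gain is 0.6 × 3/1.5 = 1.2. The bias is about 1.2 × (−0.236) = −0.28 kg.
- Simulation, 5,000 runs per cell:

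| Dropout at 30% missing | Completers, kg (95% CI coverage) | Likelihood estimate using phase 1, kg (coverage) |
|---|---|---|
| Early gainers leave more (b = +0.35) | 2.73 (88%) | 3.00 (95%) |
| Unrelated (b = 0) | 3.00 (95%) | 3.00 (95%) |
| Early gainers leave less (b = −0.35) | 3.26 (88%) | 3.00 (95%) |

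The bias is about 0.27 kg, against a completers' SE of 0.341 kg. With unrelated dropout the likelihood estimate lowers that SE only to 0.324.

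**4. Range.** Numerical integration covered 648 combinations: 10–40% missing, b of ±0.2 to ±0.5, early SD 1–2.5 kg, late SD 2–4 kg, correlation 0.3–0.9. The completers' mean runs from 1.62 to 4.38 kg, and the two ends need every input at its limit. Median absolute bias is 0.17 kg, with 10th to 90th percentiles of 0.05 to 0.51 kg. About three quarters of the combinations lie below 0.34 kg.

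**5. Dropout tied to quit status.** Assume half quitters and half smokers by phase 1 status, 6-month gains of 5 and 1 kg (cohort mean 3.00), and 15% and 45% missing (30% overall). Completers average (0.5 × 0.85 × 5 + 0.5 × 0.55 × 1)/0.70 = 2.40/0.70 = 3.43 kg. The mixed-model estimates are:

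| Assumed early gain, quitters/smokers (kg) | Phase only | Phase 1 status added |
|---|---|---|
| 1.5/1.5 | 3.43 | about 3.00 |
| 2/1 | 3.27 | about 3.00 |
| 2.5/0.5 | 3.12 | about 3.00 |

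A model with phase alone removes between none and about 70% of this bias, since (3.43 − 3.12)/0.43 = 72%. Status has to be in the model.

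**6. Dropout tied to the unseen 6-month gain.** At 30% missing and ±0.2 per kg, completers average 2.49 or 3.50 kg, and the likelihood estimate using phase 1 weight gives 2.67 or 3.33 kg. Bias is reduced but not removed.

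**The case against.** The strongest objection is that loss to follow-up is not shown. The text is in the past tense and does not say whether 108 were enrolled or completed. If all were seen at phase 2, the choice of model leaves the mean changes as they are. If 108 are the completers, an illustration with about 76 completers does not describe this study. This stands, and it limits any claim about size.

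The pooled 6-month change is also not the contrast closest to the study's title. For quitters against smokers by phase 1 status, with an assumed true difference of 4.00 kg and the same dropout slope in both groups, completers and likelihood both give 4.00. Only when slopes differ do completers move: to 3.73 or 4.27 with a slope in quitters alone, and to 3.46 or 4.53 with opposite slopes. This stands too.

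On SE, the SD can be recovered as SE × √n wherever n is reported, and no test result changes. That makes it a reporting fault, but the sentence is still wrong.

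A reader might infer that phase 1 data are wasted altogether. They are not: every post-workshop result is compared with baseline, so phase 1 enters the 0-to-1 comparison. A reader might also infer that the 6-month result is biased in a known direction. The documents support neither a direction nor an amount.

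**Conclusion.** Both parts hold, at moderate weight. The misuse of SE is certain from the text and needs no assumption. The omission of people lost before phase 2 follows from the tests named and the absence of a missing-data rule, but its effect here is unknown. Under the assumed central case, the completers' mean is off by about 0.27 kg in either direction, and 95% intervals cover about 88% of the time. It is zero if dropout is unrelated to gain or follow-up is complete.

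The central bias is below one SE, so it bears on the size of the weight change and its interval. It gives no ground for saying that a real gain would be missed or a false one found. Nor would any mixed model do: the likelihood estimate stays at 3.00 kg in the central case because dropout there depends on early gain alone. When dropout follows quit status, a model without status keeps much or all of the bias.

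**What to change.** 1. Describe distributions by SD, or by median and IQR if skewed, in both arms. Keep SE or 95% CIs for means and changes.
2. For each prospective outcome, replace the two-set tests with a linear mixed model over phases 0, 1 and 2, with unstructured covariance within participant and all available visits. Include phase 1 smoking status and its interaction with phase.
3. Report the 0-to-1 and 0-to-2 changes by phase 1 status and averaged over the whole cohort, with 95% CIs. Give the number seen at each phase, and say whether 108 were enrolled or completed.
4. Add a sensitivity analysis that shifts the missing 6-month values up and down by stated amounts.

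**Cost.** A few sentences in the analysis section and a re-run with no new data; the plan already states "Data was analyzed using JMP Pro 12 and R software". With complete follow-up the mean changes are the same as now.

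**Downsides.** The model assumes missing at random given status and earlier weights; if dropout depends on the unseen 6-month gain, some bias remains, which is why step 4 is needed. It cannot recover people without a phase 2 status for comparisons by that status. Anyone without a phase 1 status also needs a stated rule.

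### Retrospective arm: no step is described for lipid- or glucose-lowering drug changes between the two blood tests, so such changes enter the pre/post difference in the outcomes they act on

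*Combined protocol and SAP*

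**What the plan says.** Under the retrospective Study design, "Two blood test results, as documented in medical files, were collected and analyzed". The timing is "The first one during the year preceding the smoking cessation workshops" for the baseline test, "and the second during the year after completing them" for the follow-up. Metabolic measurements lists the outcomes: fasting glucose, total cholesterol (TC), HDL, LDL and triglycerides, all from routine file records. Patients are classed as smokers (S) or quitters (Q) after a telephone call.

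The only drugs mentioned for this arm are cessation aids: "The effect of smoking cessation medications on metabolic profile was also examined". The exclusions concern benign tumours, bariatric procedures and patients who could not be reached by telephone.

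Statistical Analysis states a self-controlled comparison: "each post workshop result was compared with the pre workshop result". It lists t-test/ANOVA, Wilcoxon signed rank, Mann-Whitney and Fisher tests, two-sided at 0.05. No covariate-adjusted model is named. For independent groups it says that "for unmatched sets-, the Mann Whitney's u-test was used", but it does not say that the change in Q is tested against the change in S.

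**The concern.** Using each patient as the control removes whatever stays fixed, including therapy that is the same at both tests. It does not remove a therapy change between them. The outcomes are the quantities that lipid- and glucose-lowering drugs are prescribed to alter, and the interval is long enough for prescriptions to change.

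The direction depends on the drug and the outcome. A lipid-lowering start lowers LDL and TC, a glucose-lowering start lowers glucose, and a stop does the reverse. HDL does not follow that direction, and not every drug class moves every outcome.

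A fall in LDL or glucose among quitters could thus be read as a benefit of quitting when it reflects treatment. A real rise after quitting could also be offset and missed. The study title speaks of an effect of cessation, and the outputs described would not let a reader tell these explanations apart.

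**Working it through.** **Text check.** Lipid- or glucose-lowering drugs appear nowhere in the retrospective arm or Statistical Analysis, whether as an extracted field, exclusion, stratum, covariate or sensitivity analysis. The health questionnaire under Anthropometric measurements belongs to the prospective arm and does not fill the gap.

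**No stated figure to reproduce.** The plan gives no power, effect size or SD. What follows is an illustration for LDL drug starts only; the other four outcomes are not quantified.

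**Inputs.** From the documents: 200 files and two-sided 0.05. Assumed: mean LDL 130 mg/dL; a starter's LDL falls 30-40%, so d = 130 × 0.30 = 39 to 130 × 0.40 = 52 mg/dL; SD of change without drug starts 25 or 35 mg/dL; 100 patients per group; no true cessation effect.

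**Formulas.** With a share p starting, false shift = p × d and SD = √(SD₀² + p(1−p)d²). For Q versus S, false difference = (p_Q − p_S) × d. Rejection rates come from the noncentral t (paired or Welch).

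**One cell of each (d = 39, SD₀ = 25).**
- Quitters alone, p = 10%: shift 3.9; SD = √(625 + 0.09 × 1521) = 27.6; standard error 2.76; noncentrality 1.41; rejection 29%.
- Q 10% versus S 5%: difference 0.05 × 39 = 1.95; standard error = √(761.9/100 + 697.2/100) = 3.82; noncentrality 0.51; rejection 8%.

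**False-positive rates (nominal 5%).**

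| Comparison | Starting a drug | False shift, mg/dL | SD 25 | SD 35 |
|---|---|---|---|---|
| Quitters alone, paired t | 1-2% | 0.4-1.0 | 5-7% | 5-6% |
| | 5% | 2.0-2.6 | 11-16% | 8-11% |
| | 10% | 3.9-5.2 | 29-42% | 18-27% |
| Q versus S, Welch | equal | 0 | 5% | 5% |
| | 2% v 1% | 0.4-0.5 | 5% | 5% |
| | 10% v 5% | 2.0-2.6 | 8-10% | 7-8% |
| | 15% v 5% | 3.9-5.2 | 17-24% | 12-16% |

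**Sensitivity.**
- Rank tests (simulation, 20,000 studies per cell). Signed rank at 10% starting: 22-29% (SD 25), 16-21% (SD 35). Mann-Whitney at 10% v 5% and 15% v 5%: about 7-8% and 15-18% (SD 25), 6-7% and 11-14% (SD 35).
- A 60/140 split of the 200 files, either way, Welch, SD 25: 7-9% and 15-22%.
- Stops, modelled as a rise of d, offset starts. Quitters alone, 10% starting and 5% stopping: 10-13% (SD 25). With 5% and 5%: back to 5%.
- Masking of a true 5 mg/dL rise in quitters alone (net shift 5 − p × d): detection is 51% with no starts, 33-37% at 2% and 14-21% at 5% (SD 25); 29%, 19-22% and 9-13% (SD 35).

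**The case against.** The case against has several parts.

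- **Silence in a short text.** This is a brief, past-tense methods summary, so silence is weak evidence. That stands. A reader might infer that prescription data were never looked at, or that the results are in fact distorted by drugs. The documents support neither; they show only that no such step is described.
- **Smokers as a comparator.** Classing patients as S and Q and listing a test for unmatched sets make a comparison of changes plausible. On that reading the distortion is small unless uptake is clearly unequal, and nothing in the documents points to such an imbalance. This stands as to size. But the comparison is not specified, and it removes only drug change that is equal in the two groups.
- **Medicines were examined.** Only cessation medicines were, so this does not answer the point.
- **Other time-varying factors.** Diet, weight and regression to the mean affect any uncontrolled pre/post comparison too. True, and the quitter-smoker comparison helps with whatever is shared. Drug changes merit separate mention because they act directly on these outcomes and may be recoverable from the same files.
- **Assumed inputs.** Everything in the illustration except alpha and the total of 200 is assumed. This stands. The 42% figure needs quitters tested alone, 10% starting, no stops and the larger drug effect with the smaller SD; it is not an estimate for this study.
- **Post-baseline adjustment.** A drug start may respond to the first test or to quitting, so conditioning on it can itself bias. This stands and shapes the fix.

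**Conclusion.** The point holds in limited form. Followed as written, the self-controlled comparison absorbs any lipid- or glucose-lowering drug change between tests into the apparent effect of cessation on the outcome that the drug acts on. That is a bias in the stated comparison, not merely a missing detail.

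Its size cannot be derived from the documents and runs from negligible to large. It depends on uptake, on offsetting stops, on balance between Q and S, and on which comparison is treated as the main one, which the plan does not say. Low or balanced uptake is nearly harmless; moderate uptake in quitters analysed alone is not.

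It would go too far to infer that every drug start lowers every outcome (HDL is the clear exception), or that an observed change in quitters must be a drug effect. The omission from the text is certain and its consequence is not, so this is a change that should be made, held with medium confidence.

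**What to change.** 1. Make the main retrospective comparison the change in Q versus S, adjusted for the baseline value, which is already collected.
2. From the same files, extract lipid- and glucose-lowering prescriptions at both test dates, and report starts, stops and changes by Q and S.
3. Show a sensitivity analysis, adjusted for drug change or limited to patients with unchanged therapy, beside the all-patient result and not in place of it.
4. If the two disagree, or the prescription data cannot be obtained, say so and report the result as an association.

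If this was already done, describing it would settle the omission.

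The cost is a return to up to 200 files for a few fields, since the test results are already collected. The unchanged-therapy subset will be smaller and less precise. Because drug change is post-baseline, the sensitivity analysis carries its own risk of bias and may not settle the question.
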